#### 6. STUDY PARAMETERS

#### 6.1. Pharmacokinetic Parameters

The follow pharmacokinetic parameters will be calculated on the varenicline plasma levels:

### 7. STUDY MATERIALS

#### 7.1. Drug Supply

• Treatment A: Single oral tablet of 1 mg varenicline (Chantix®)

Chantix® is supplied as 1 mg capsular biconvex, light blue film-coated tablet debossed with "*Pfizer*" on one side and "CHX 1.0" on the other side.

- Treatment B: OC-01 (varenicline) Nasal Spray delivered as a 50 µL spray (0.06 mg per each 50 µL spray) into each nostril for a total delivered dose of 0.12 mg.
  - OC-01 (varenicline) Nasal Spray will be formulated at the desired concentration in sodium phosphate buffers and sodium chloride as an aqueous solution and presented in an amber glass vial with a multi-use preservative-free nasal pump.
  - OC-01 (varenicline) Nasal Spray is preservative-free and intended for intranasal use only. The product should not be used if cloudy or if particulate matter are present.
  - OC-01 solution must be administered without dilution.

#### 7.2. Other Study Supplies

Intranasal speculums

#### 8. STUDY METHODS AND PROCEDURES

#### 8.1. Participant Entry Procedures

#### 8.1.1. Overview

Participants as defined by the criteria in Sections 5.2, 5.3, and 5.4 will be considered for entry into this study.

#### 8.1.2. Informed Consent

Prior to a participant's enrollment in the trial (i.e., prior to any study-related procedures), the study will be discussed with each potential participant and participants wishing to participate must be administered and provide written informed consent using an Institutional Review Board (IRB)-approved informed consent form (ICF). The ICF must be the most recent version that has received approval by a properly constituted IRB.

#### 8.1.3. Washout Intervals

Prohibited medications, treatments, and activities are outlined in the Exclusion Criteria (Section 5.4).

#### 8.1.4. Procedures for Final Study Entry

Subjects must meet all inclusion criteria and none of the exclusion criteria.

#### 8.1.5. Methods for Assignment to Treatment Groups

Each subject who enters the screening period for the study (defined as the point at which the subject signs the informed consent form (ICF) receives a unique subject identification number before any study-related activities/procedures are performed. This number will be used to identify the subject throughout the clinical study and must be used on all study documentation related to that subject. The subject identification number must remain constant throughout the entire clinical study.

Subjects who meet the eligibility requirements will be randomly assigned to receive Treatment A or Treatment B during Treatment Period 1. For Treatment Period 2, subjects will receive the alternate treatment not received during Treatment Period 1.

#### 8.2. Concomitant Therapies

#### 8.2.1. Prohibited Medications/Treatments

Disallowed medications/treatments during the study are outlined in the Exclusion Criteria (Section 5.4)

#### 8.2.2. Escape Medications

No escape medication is required for this study.

#### 8.2.3. Special Diet or Activities

Subjects must be in a fasted state overnight and abstain from alcohol for 24 hours prior to each study period until after the last sample is collected from each study period.

#### 8.3. Examination Procedures

## 8.3.1. Procedures to be Performed at Each Study Visit with Regard to Study Objective(s)

The following procedures will be performed (see Appendix 2 for description). Repeat assessments can be performed at the discretion of the investigator.

#### Screening/Visit (Day -28 to -2):

- Informed consent/Health Information Portability and Accountability Act (HIPAA) consent
- Demographic data, medical history, concomitant medications
- Eligibility Criteria
- Urine pregnancy test (if applicable)
- Drug and Alcohol Screen
- Physical Examination
- 12-lead ECG
- Vital Signs
- Laboratory samples (hematology, chemistry)

- Urinalysis
- Intranasal Examination

#### Period 1 Check-In (Day -1)

- Serum pregnancy test (if applicable)
- Drug and Alcohol Screen
- Intranasal Examination
- Concomitant Medications

#### **Period 1 (Day 1-6):**

- Vital Signs (pre-treatment and 2 hours post treatment administration)
- Laboratory Samples (chemistry 2 hours post treatment administration)
- Randomization
- Administration of OC-01 (varenicline) Nasal Spray or Chantix®
- PK Sample Collection
- Concomitant Medications
- AE Query

#### Period 2 Check-In (Day 14)

- Serum Pregnancy Test (if applicable)
- Drug and Alcohol Screen
- Intranasal Examination
- Concomitant Medications
- AE Query

#### Period 2 (Day 15-20):

- Vital Signs (pre-treatment and 2 hours post treatment administration)
- Laboratory Samples (chemistry 2 hours post treatment administration))
- Administration of OC-01 (varenicline) Nasal Spray or Chantix®
- PK Sample Collection
- Concomitant Medications
- AE Query

#### End of Study/Early Termination (Day 27 + 7):

- Urine pregnancy test (if applicable)
- Physical Examination
- 12-lead ECG
- Vital Signs
- Laboratory Samples (hematology, chemistry)
- Urinalysis
- Intranasal Examination
- Concomitant Medications
- AE Query

#### 8.4. Pharmacokinetic Sampling Schedule

PK samples should be collected according to the following schedule during Treatment Period 1 and Treatment Period 2:

All times are after study drug administration except for predose (time 0)

#### **In-Unit Blood PK Sampling**

Sample 1: Predose (time 0) Sample 2: 5 minutes Sample 3: 15 minutes Sample 4: 30 minutes Sample 5: 1 hour Sample 6: 2 hours Sample 7: 3 hours Sample 8: 4 hours Sample 9: 6 hours Sample 10: 8 hours Sample 11: 12 hours Sample 12: 24 hours Sample 13: 36 hours Sample 14: 48 hours

#### **Out-Patient Blood PK Sampling**

Sample 15: 72 hours Sample 16: 96 hours

OPP-100 Protocol Amendment #2

Sample 17: 120 hours

#### 8.5. Schedule of Visits, Measurements and Dosing

#### 8.5.1. Scheduled Visits

Refer to Appendix 1 for a schedule of visits and measurements.

#### 8.5.2. Unscheduled Visits

These visits may be performed in order to ensure subject safety. All procedures performed at an unscheduled visit will be recorded in the source.

Evaluations that may be conducted at an Unscheduled Visit include:

- Intranasal Examination
- Physical Examination
- Vital Signs
- 12 lead ECG
- Laboratory assessments/urinalysis
- Urine pregnancy test (if applicable)
- Assessment of AEs
- Assessment of concomitant medications and/or treatments
- Any other assessments needed in the judgment of the investigator

#### 8.6. Compliance with Protocol

Oyster Point Pharma, Inc. will not compensate the Investigator for evaluation of cases in which the procedures and evaluations are conducted in a manner other than that specified in the protocol.

The investigator will conduct the trial in compliance with the protocol and approved by the IRB/IEC and the appropriate regulatory authority(ies). Modifications to the protocol are not to be made without agreement of both the investigator and Oyster Point Pharma, Inc. Changes to the protocol will require written IRB/IEC approval prior to implementation, except when the modification is needed to eliminate an immediate hazard(s) to subjects. When immediate deviation from the protocol is required to eliminate an immediate hazard(s) to patients, the investigator will contact Oyster Point Pharma, Inc. Any departures from the protocol must be documented.

#### 8.7. Subject Disposition

#### 8.7.1. Completed Subjects

A completed subject is one who has completed both the Period 1 and Period 2 study visits and has received treatment with both OC-01 (varenicline) Nasal Spray and Chantix®.

#### 8.7.2. Discontinued Subjects

Subjects may be discontinued from treatment, or from involvement in the study at any time prior to their completion of the study due to:

- AEs
- Protocol violations
- Lost to follow-up
- Pregnancy
- Physician decision
- Subject non-compliance
- Sponsor termination of study
- Withdrawal by subject
- Other reasons

Note: In addition, any subject may be discontinued from treatment or from study involvement from any sound medical reason at the discretion of the investigator (after consultation with the Sponsor) or Sponsor.

Notification of a subject discontinuation and the reason for discontinuation will be made to the Sponsor and/or its designee and will be clearly documented.

Discontinued subjects will not be replaced.

#### 8.8. Study Termination

The study may be stopped at any time by the Investigator and/or after consultation with the Sponsor, with appropriate notification.

#### 8.9. Study Duration

An individual subject's participation will involve ten visits over approximately 60 days.

#### 8.10. Monitoring and Quality Assurance

# 9. SAFETY DEFINITIONS, SAFETY MONITORING AND REPORTING

#### 9.1. Adverse Event

An adverse event (AE) is defined as any untoward medical occurrence associated with the use of a drug in humans, whether or not the event is considered drug-related. An AE can therefore be any unfavorable and unintended sign (e.g., an abnormal laboratory finding), symptom, or disease occurring after the subject started dosing with the study drug, without any judgment about causality. Any pre-existing medical condition that worsens after administration of the study drug will also be considered a new AE.

Study drug includes the investigational drug under evaluation. Documentation regarding the AE should be made as to the nature, date of onset, end date, severity, expectedness relationship to study drug, action(s) taken, seriousness, and outcome of any sign or symptom observed by the Investigator or reported by the subject upon indirect questioning. AE collection will start following the first administration of study drug until the last follow up visit of the study.

#### 9.1.1. Severity

Severity of an AE is defined as a qualitative assessment of the degree of intensity of an AE as determined by the investigator or reported to him/her by the patient/subject. The assessment of severity is made irrespective of relationship to study drug or seriousness of the event and should be evaluated according to the following scale:

• *Mild:* Event is noticeable to the subject, but is easily tolerated and does not interfere with the subject's daily activities.

- *Moderate*: Event is bothersome, possibly requiring additional therapy, and may interfere with the subject's daily activities.
- *Severe*: Event is intolerable, necessitates additional therapy or alteration of therapy, and interferes with the subject's daily activities.

#### 9.1.2. Relationship to Study Drug

The relationship of each AE to the investigational product should be determined by the investigator using these explanations:

- *Definite:* When there are good reasons and/or sufficient documentation to demonstrate a direct causal relationship between investigational product and AE
- *Probable:* When there are good reasons and/or sufficient documentation to assume a causal relationship in the sense of plausible, conceivable, likely but not necessarily highly probable
- *Possible:* When there is sufficient information to accept the possibility of a causal relationship in the sense of not impossible and not unlikely, although the connection is uncertain or doubtful, for example; due to missing data or insufficient evidence.
- *None:* When there is sufficient information to accept a lack of a causal relationship, in the sense of impossible and improbable.
- *Unclassified:* When the causal relationship is not assessable for whatever reason due to insufficient evidence, conflicting data or poor documentation.

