#### SPONSOR PERSONNEL

### SYNOPSIS

Protocol Title:	An Open-Label, Single-Center, Randomized, 2-way Crossover Study to Evaluate the Relative Bioavailability of Varenicline Administered as OC-01 Nasal Spray as Compared to Varenicline Administered Orally as Chantix ®					
Protocol Number:	OPP-100					
Investigational Product:	OC-01 (varenicline) Nasal Spray					
Study Objectives:	Primary Objective: To assess the relative bioavailability of varenicline administered intranasally at its highest intended clinical strength compared to varenicline administered orally at its highest oral tablet strength.					
	Secondary Objective: To assess the clinical and laboratory safety of varenicline administered as a single dose orally and intranasally.					
	Overall Study Design					
Structure:	This is an open label, single dose, randomized, 2-way crossover study					
	Subjects will attend the unit for a screening assessment up to 28 days prior to the first dose.					
	Subjects who are eligible for the study will return to the unit for 2 in-unit treatment periods, each separated by a minimum of 14 days.					
	An End of Study visit will occur 7-14 days after the final dose.					
	The two study treatments are:					
	• Single oral dose of 1 mg varenicline (Chantix ® ).					
	
 
Intranasal dose of 0.12 mg OC-01 (varenicline)- delivered as a 50 μL (0.06 mg) spray into each nostril
 
					
	Treatment Period 1: Subjects will be admitted and will be randomly assigned to receive a single dose of varenicline either orally or intranasally. The administration dose will be delivered after an overnight fast by the subject.					
	PK samples will be collected pre-dose and in an intensive sampling regimen up to 120 hours post-dose to allow for the assay of varenicline.					
	Treatment Period 2: This period will be identical to Treatment Period 1 except that the administration of varenicline will be via the intranasal					

	
 
route for those subjects that previously received varenicline via the oral route. Those subjects that were previously administered oral varenicline during Treatment Period 1 will receive varenicline via the intranasal route.
 
End of Study Visit will occur 7-14 days after the final period's dose of varenicline when follow-up assessments will be performed.
 
					
Duration:	10 study visits over a period of approximately 60 days:					
	Screening: Day -28 to -2					

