#### 9.1.3. Expectedness

The expectedness of an AE should be determined based upon existing safety information about the study drug using these explanations:

- *Unexpected:* An AE that is not listed in the Investigator's Brochure (IB) or is not listed at the specificity or severity that has been observed.
- *Expected:* An AE that is listed in the IB at the specificity and severity that has been observed.
- *Not Applicable:* Any AE that is unrelated to the study drug.

AEs that are mentioned in the IB as occurring with a class of drugs or as anticipated from the pharmacological properties of the drug but are not specifically mentioned as occurring with the particular drug under investigation are to be considered unexpected.

The investigator should initially classify the expectedness of an AE, but the final classification is subject to the Medical Monitor's determination.

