### 13.2 ADVERSE EVENTS

Adverse events (AEs) will be coded using the Medical Dictionary for Regulatory Activities (MedDRA) version 22.0.

A treatment-emergent AE is any AE occurring after the administration of the study drug and within 5 days after study drug administration, or a pre-treatment AE or pre-existing medical condition that worsens in intensity after start of the study drug and within the time of residual drug effect in both periods.

All AE data will be listed by subject. Only treatment-emergent AEs will be presented in summary tables by treatment.

For treatment emergent AEs overview summary table, by treatment and overall, will be prepared and including number of subjects reporting an AE, the percentage of subjects (%) with an AE and the following categories:

- Any Treatment-emergent adverse events (TEAEs)
- Deaths
- Serious TEAEs
- Study drug related TEAEs
- TEAEs leading to withdrawal
- TEAEs leading to death

Summaries of the following TEAEs will be provided by system organ class (SOC) and preferred term (PT):

- All TEAEs
- Study drug related TEAEs
- Serious adverse events (SAEs)
- TEAEs by severity

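### Does grading causality against the investigational product mean that adverse events after oral Chantix would be recorded as unrelated?

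*Protocol*

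**What the plan says.** The Synopsis has a field "Investigational Product" whose entry is "OC-01 (varenicline) Nasal Spray". Chantix appears separately, as Treatment A.

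The section headed "9.1.2. Relationship to Study Drug" gives the causality instruction: "The relationship of each AE to the investigational product should be determined by the investigator using these explanations". Its grades run from *Definite* to *None*, with *Unclassified* for events that cannot be assessed.

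Protocol 9.1 says of the term study drug only that "Study drug includes the investigational drug under evaluation". The same section lists what must be documented for each event: "severity, expectedness relationship to study drug, action(s) taken, seriousness, and outcome of any sign or symptom".

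Protocol 9.1.3 defines an expected event as "An AE that is listed in the IB at the specificity and severity that has been observed", where IB is the Investigator's Brochure.

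SAP 13.2 presents treatment-emergent events by treatment. "Study drug related TEAEs" is both a line of the overview table and a summary by system organ class and preferred term.

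**The concern.** The causality instruction uses a term that the Synopsis attaches to the nasal spray alone, whereas the SAP table needs a grade against whichever treatment the subject has just taken. If an investigator followed 9.1.2 to the letter, an event after Chantix in a subject not yet given OC-01 could not be related to OC-01 and would be graded *None*. The related-event table would then set a real count for the spray beside a count for the tablet that was too low by construction.

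The secondary objective covers the safety of both routes. A distorted table would make the spray look worse than the tablet and hide drug-related events of the tablet. The grade also feeds expectedness (9.1.3) and the reporting of suspected unexpected reactions (9.3.1).

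**Working it through.** The plan gives no figure to reproduce, and the visible text gives no AE rate. The check is a comparison of texts plus two small sums.

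**Size of the group under the literal reading.** About 22 subjects (Protocol 5.1) are randomised 1:1 to two sequences (SAP 3.4): 22 / 2 = 11 take Chantix first. In their Period 1 no OC-01 has been given, so related events would number 0 on that reading. The other 11 took OC-01 at least 14 days before Chantix. This bounds who could be affected. It does not estimate how many events would be misgraded.

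**Does study drug in the AE rules mean OC-01 only?**

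1. Protocol 9.1 starts AE collection after the first administration of study drug. If that meant OC-01, the 11 Chantix-first subjects would have no AE collection in Period 1. Yet Protocol 8.3.1, Protocol Appendix 1 and SAP Table 1 schedule an AE query in Period 1 for every subject.
2. SAP 6.1 sets Day 1 at the first dose of study drug. For a Chantix-first subject under the OC-01-only reading, Day 1 would move to the Period 2 dose, which the schedule calls Day 15. The Chantix dose would fall on study day 1 − 15 = −14, although the schedule places Period 1 on Days 1–6.
3. Protocol 8.4 times PK samples from study drug administration in both periods. Protocol 11.5.3 opens with OC-01/Chantix and then calls them the study drugs. SAP 13.6 takes a baseline before the study drug dose of each period.

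The term therefore covers both products. The sentence in 9.1 is consistent with this: it says what study drug includes and does not exclude Chantix.

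**Does investigational product in 9.1.2 mean something narrower?** The heading of 9.1.2 says study drug, 9.1 requires the relationship to study drug to be documented, and 9.1.3 reserves its not-applicable category for events unrelated to the study drug. All three treat the 9.1.2 grade as a grade against study drug. The simplest account is that the body text uses a loose synonym. The Synopsis field identifies the product under development; it does not set a rule for grading.

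**Is *None* a default?** No. It requires sufficient information to accept that there is no causal relationship, and nothing tells the investigator to assign it after Chantix. Both products contain varenicline.

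**Can each event be assigned to a treatment?** SAP 13.2 counts new events as treatment-emergent within 5 days of a dose, and doses are at least 14 days apart. The window closes at least 14 − 5 = 9 days before the next dose, so a new-onset event belongs to one dose only. Onset date (Protocol 9.1) and dosing time (SAP 13.1) are both recorded.

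**What does not depend on the grade?** The by-treatment tables of all treatment-emergent events and the listing of all events (SAP 13.2), the reporting of all events to the sponsor (Protocol 9.3), the reporting of serious events regardless of relationship (Protocol 9.3.2), and the PK comparison.

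**The case for a change.** The best case for the concern is that 9.1 is the only place in the safety section that explains study drug, and a site that looks there is pointed back to the investigational drug, with no mention of Chantix. The plural use that covers both products is in the accountability section, which an investigator grading an event may not consult. On the literal reading the strict wording of *None* is met in Period 1 of the Chantix-first sequence, since a relationship to a product not yet given is impossible. An event graded that way would become not applicable for expectedness and leave the suspected-and-unexpected pathway. The Medical Monitor has the final word on expectedness, but no such check on causality is visible. The finished table would not show which reading had been used.

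Part of this stands. Section 9.1.2 does mix two terms, and 9.1.3 visibly names only the Investigator's Brochure as its reference. The step from there to events being recorded as unrelated does not stand. It needs the narrowest sense of one phrase, against the section's own heading and the documentation requirement in 9.1. The claim that up to all Chantix-related events could be lost restates that assumption and measures nothing. On expectedness, 9.1.3 begins from existing safety information about the study drug, and the Brochure, which is not among these documents, may cover oral varenicline.

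**Conclusion.** The inconsistency of terms is real but clerical, and no change to the plan follows. The documents do not show that events after Chantix would be graded unrelated or that the comparison of routes would be distorted. If a site did apply the literal reading, the clearest exposure would be Period 1 of about 11 of 22 subjects. The effect would be confined to one overview row and one summary by organ class and preferred term, both descriptive, in a study that tests no formal hypothesis. If the site grades against the dose just given, the effect is nil.

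This rests on two assumptions: that investigators read 9.1.2 in line with its heading and with 9.1, and that the case report form asks for relationship to study drug as 9.1 requires. The form, the table specifications and parts of the SAP are not visible, so neither assumption can be confirmed here. A single shared definition of study drug would be tidier, but it would not alter what is collected or how it is tabulated.

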#### 9.1.3. Expectedness

The expectedness of an AE should be determined based upon existing safety information about the study drug using these explanations:

- *Unexpected:* An AE that is not listed in the Investigator's Brochure (IB) or is not listed at the specificity or severity that has been observed.
- *Expected:* An AE that is listed in the IB at the specificity and severity that has been observed.
- *Not Applicable:* Any AE that is unrelated to the study drug.

AEs that are mentioned in the IB as occurring with a class of drugs or as anticipated from the pharmacological properties of the drug but are not specifically mentioned as occurring with the particular drug under investigation are to be considered unexpected.

The investigator should initially classify the expectedness of an AE, but the final classification is subject to the Medical Monitor's determination.

